### 7.5.1.1. Criteria for the Calculation of Apparent Terminal Elimination Rate Constant and Half-life

The start of the terminal elimination phase for each subject will be defined by visual inspection and generally will be the first point at which there is no systematic deviation from the log-linear decline in concentrations.

The apparent terminal elimination rate constant ( $\lambda_z$ ) will only be calculated when a reliable estimate can be obtained using at least 3 data points, preferably not including  $C_{max}$ , and the adjusted coefficient for determination of exponential fit ( $R^2$ -adj) of the regression line is  $\geq 0.7$ . Parameters requiring  $\lambda_z$  for their calculation (eg,  $AUC_{0-\infty}$ ,  $t_{1/2}$ ,  $CL/F$  and  $V_z/F$ ) will only be calculated if the  $R^2$ -adj value of the regression line is  $\geq 0.7$ .

The following regression-related diagnostic PK parameters will be determined, when possible:

Parameter	Units	Definition
$\lambda_z$	1/h	apparent terminal elimination rate constant
$\lambda_z$ Upper	h	end of exponential fit
$\lambda_z$ Lower	h	start of exponential fit
$\lambda_z$ N	NA	number of data points included in the log-linear regression
$\lambda_z$ Span Ratio	NA	time period over which $\lambda_z$ was determined as a ratio of $t_{1/2}$
$R^2$ -adj	NA	adjusted coefficient for determination of exponential fit

Where possible, the span of time used in the determination of  $\lambda_z$  (ie, the difference between  $\lambda_z$  Upper and  $\lambda_z$  Lower) should be  $\geq 2$  half-lives. If the  $\lambda_z$  Span Ratio is  $< 2$ , the robustness of the  $t_{1/2}$  values will be discussed in the CSR.

### 7.5.1.2. Criteria for Calculation and Reporting of Area Under the Concentration-time Curve

The minimum requirement for the calculation of AUC will be the inclusion of at least 3 consecutive concentrations above the lower limit of quantification. If there are only 3 consecutive concentrations, at least 1 should follow  $C_{max}$ . An exception may be made for metabolites, where  $C_{max}$  may be the last timepoint.

If the extrapolated area is  $> 20\%$ ,  $AUC_{0-\infty}$  (and derived parameters) may be excluded from the summary statistics and statistical analysis at the discretion of the sponsor or pharmacokineticist.

If  $AUC_{0-\infty}$  cannot be determined reliably for all subjects and/or dose levels, an alternative AUC measure, such as AUC to a fixed timepoint, may be used in the statistical analysis of dose proportionality/food effect.

### **7.5.1.3. Criteria for Handling Concentration Below the Limit of Quantification or Missing Concentrations for Pharmacokinetic Analysis**

Plasma concentrations below the limit of quantification (BLQ) will be assigned a value of 0 before the first measurable concentration and thereafter BLQ concentrations will be treated as missing. The following rules apply to the specific situations defined below:

- If an entire concentration-time profile is BLQ, it will be excluded from PK analysis.
- Where 2 or more consecutive concentrations are BLQ at the end of a profile, the profile will be deemed to have terminated and any further quantifiable concentrations will be set to missing for the calculation of the PK parameters, unless they are considered to be a true characteristic of the profile of the drug.
- If a predose analyte concentration is missing, following a single dose (Part A) or Day 1 dose (Part B) it will be set to 0 by default within Phoenix WinNonlin.
- For multiple dose part of the study (Study Profile Day 7), if the analyte concentration at the end of the dosing interval ( $\tau$ ) is missing, this may be substituted with the predose concentration. Similarly, if the predose concentration is missing then this may be substituted with the concentration at  $\tau$ .

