### 3.1.2. Part B (Multiple Ascending Dose)

Part B will comprise a multiple-dose, sequential group, escalating-dose design conducted in healthy adult male and female subjects. Part B may start prior to completion of all planned dose groups in Part A, at a dose equal to or less than that evaluated as safe and well tolerated in Part A.

A total of approximately 24 subjects are planned to be studied in 3 groups (Groups B1 to B3). In each group, 6 subjects will receive AQ280 and 2 subjects will receive placebo. Each group should contain both male and female subjects, preferably at least 2 subjects of each gender. Additional groups may be added based on the need for more evaluations or groups removed based on data obtained.

There will be a minimum of 9 days between dose escalations for each group.

Potential subjects will be screened to assess their eligibility to enter the study from 2 days up to 5 weeks before the first dose of AQ280 or placebo. Each subject will participate in 1 group only and reside at the study site from Days -1 to 9.

For all subjects, dosing is planned to be once daily (QD) on Days 1 to 7, inclusive, at approximately the same time each morning. The dosing regimen in Part B may be changed following review of preliminary data from groups in Part A or previous groups in Part B. The daily dose administered, when given repeatedly, will be predicted to not exceed an exposure shown to be safe and well tolerated in Part A. Dietary state will be determined based on data obtained in Part A.

A safety follow-up visit will be conducted 1 week ( $\pm 3$  days) after the final dose.

Based on the ongoing review of the safety, tolerability, and PK results, additional outpatient visits may be required.

[figure not shown]
Safety assessments will include AE reporting, vital signs, ECGs, clinical laboratory tests, and physical examination.

Blood samples to determine the PK of AQ280 and its main metabolite, AQ282, will be collected from predose up to 24 hours postdose on Day 1; predose on Days 3 through 6; and from predose up to 48 hours postdose on Day 7.

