### 7.1.2. Calculation of the Summary Statistics

For continuous data the following rules will be applied:

- Missing values will not be imputed, unless specifically stated otherwise.
- Unrounded data will be used in the calculation of summary statistics.
- If the number of subjects with valid observations ( $n < 3$ ), summary statistics will not be calculated, with the exception of  $n$ , minimum, and maximum.
- In general, as early termination data are not associated with any scheduled timepoint, they will be excluded from all calculations of summary statistics and statistical analyses. Exceptions may be made where justified.

For categorical data the following rules will be applied:

- For ordered categorical data (eg, adverse event [AE] severity), all categories between the possible minimum and maximum categories will be included, even if  $n = 0$  for a given category.
- For non-ordered categorical data (eg, race), only those categories for which there is at least 1 subject represented will be included; unless specifically stated otherwise.
- Missing values will not be imputed, unless specifically stated otherwise. A ‘missing’ category will be included for any parameter for which information is missing. This will ensure that the population size totals are consistent across different parameters.

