## 7.5. Pharmacokinetic Assessments

### 7.5.1. Pharmacokinetic Analysis

The following PK parameters will be determined where possible from the plasma concentrations of AQ280 and AQ282 using noncompartmental methods in validated software program Phoenix WinNonlin (Certara, Version 8.1.1 or higher):

Parameter	Units a	Definition
AUC 0-tlast	h*ng/mL	area under the concentration-time curve from time 0 to the time of the last quantifiable concentration (t last ) (Part A and Day 1 of Part B only) b
AUC 0-24	h*ng/mL	area under the concentration-time curve over the time interval 0 to 24 hours postdose b
AUC τ	h*ng/mL	area under the concentration-time curve over the dosing interval (Part B only) b
AUC 0-∞	h*ng/mL	area under the concentration-time curve from time 0 extrapolated to infinity c (Part A and Day 1 of Part B only)
%AUC extrap	h*ng/mL	percentage of area under the concentration-time curve due to extrapolation from the last quantifiable concentration to infinity (Part A and Day 1 of Part B only)
C max	ng/mL	maximum observed concentration
t max	h	time of the maximum observed concentration
t last	h	time of the last quantifiable concentration
C trough	ng/mL	concentration at the end of the dosing interval
t 1/2	h	apparent terminal elimination half-life
CL/F	L/h	apparent total clearance (AQ280 only)
V z /F	L	apparent volume of distribution during the terminal phase (AQ280 only)
MR AUC		metabolite:parent ratio based on AUC 0-∞
MR Cmax		metabolite:parent ratio based on C max
F rel, AUC0-∞		relative bioavailability in the fed and fasted state based upon AUC 0-∞ (Food effect group (A3) only)
F rel, Cmax		relative bioavailability in the fed and fasted state based upon C max (Food effect group (A3) only)
AR AUC		accumulation ratio based on AUC 0-τ (Part B only)
AR Cmax		accumulation ratio based on C max during the dosing interval (Part B only)
LR		Linearity ratio
DAUC 0-tlast	h*ng/mL/mg	AUC 0-tlast normalized by dose administered.
DAUC 0-24	h*ng/mL/mg	AUC 0-24 normalized by dose administered

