DAUC T	h*ng/mL/mg	AUC T normalized by dose administered (Part B only)
DAUC 0-∞	h*ng/mL/mg	AUC 0-∞ normalized by dose administered
DC max	ng/mL/mg	C max normalized by dose administered

\* Units are based on concentration units (provided by the bioanalytical lab or preferred units for presentation of PK parameters) and dose units used in the study.

b The AUC will be calculated using the linear trapezoidal rule for increasing concentrations and the logarithmic rule for decreasing concentrations (linear up/log down rule).

c Based on the last observed quantifiable concentration

d Calculated by dividing the parameter by the dose (mg)

Additional PK parameters may be determined where appropriate.

Pharmacokinetic analysis will be carried out where possible using actual dose administered (mg) and actual postdose blood sampling times. If an actual time is missing, the sample concentration result will be treated as missing unless there is scientific justification to include the result using the nominal time.

The parameters  $C_{\max}$ ,  $C_{\text{trough}}$ ,  $t_{\text{last}}$ , and  $t_{\max}$  will be obtained directly from the concentration-time profiles. If  $C_{\max}$  occurs at more than 1 timepoint,  $t_{\max}$  will be assigned to the first occurrence of  $C_{\max}$ .

The metabolite:parent ratio(s) (MRAUC or MRCmax) will be calculated as follows:

$$MR_{AUC} = (AUC_{0-\infty} [AQ282] / MW [AQ282]) / (AUC_{0-\infty} [AQ280] / MW [AQ280]),$$

where MW is the molecular weight of each analyte

$$MR_{C_{max}} = (C_{max} [AO282] / MW [AO282]) / (C_{max} [AO280] / MW [AO280]),$$

where MW is the molecular weight of each analyte

The molecular weights of AQ280 and AQ282 to be used in the adjustment are as follows:

CCI

The parameter  $AUC_{0-t_{last}}$  or other common partial area may be used to determine  $MR_{AUC}$  if  $AUC_{0-\infty}$  cannot be reliably calculated for the majority of subjects.

The accumulation ratio(s) ( $AR_{AUC}$  and  $AR_{C_{max}}$ ) will be calculated as follows:

$$AR_{AUC} = AUC_{0-1} \text{ Profile Day 7} / AUC_{0-1} \text{ Profile Day 1}$$

$$AR_{C_{max}} = C_{max} \text{ Profile Day 7} / C_{max} \text{ Profile Day 1}$$

The linearity ratio (LR) will be calculated as ratio of  $AUC_{0-\tau}$  following multiple dosing to  $AUC_{0-\infty}$  following a single dose:

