## **7.5.2. Presentation of Pharmacokinetic Data**

All PK concentrations and parameters will be listed.

Summary tables, arithmetic mean (+ standard deviation [SD]) figures, overlaying individual figures, and individual figures by treatment and time postdose will be provided for plasma PK concentrations. All figures will be produced on both linear-linear and linear-logarithmic scales, with the exception of figures across all days, which will be produced on the linear-linear scale only. The  $+SD$  bars will only be displayed on the linear-linear scale.

Summary tables by treatment will be provided for all PK parameters, with the exception of diagnostic regression-related PK parameters.

A subject may be excluded from the PK summary statistics and statistical analysis if the subject has an AE of vomiting that occurs at or before 2 times the median  $t_{max}$ .

If the actual time of sample collection deviates from the nominal time by more than  $\pm 10\%$ , the plasma concentration will be flagged and excluded from the summary statistics.

Individual concentrations deemed to be anomalous will be flagged in the listings and excluded from the summary statistics.

For plasma concentration data the following rules will apply:

- Values that are BLQ will be set to 0 for the calculation of summary statistics.
- Arithmetic mean or median values that are BLQ will be presented as 0.

For PK parameters the following rule will apply:

- Geometric mean and coefficient of variation will not be calculated for  $t_{last}$  or  $t_{max}$ .

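### The SAP has no Ctrough rule for results below the limit of quantification: a measured BLQ trough on Day 1 of Part B drops out of the Ctrough summary but counts as 0 in the concentration table, and its Day 7 handling is left open

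*SAP*

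**What the plan says.** SAP 7.5.1 lists Ctrough among the PK parameters, defined as the "concentration at the end of the dosing interval". Together with Cmax, tlast and tmax, it "will be obtained directly from the concentration-time profiles".

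SAP 7.5.1.3 governs BLQ results in the PK analysis. They are 0 before the first measurable concentration, and "thereafter BLQ concentrations will be treated as missing". For the Day 7 profile only, if the concentration at tau is missing, "this may be substituted with the predose concentration"; the reverse substitution is also allowed.

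SAP 7.5.2 says "Summary tables by treatment will be provided for all PK parameters", apart from the regression diagnostics. For plasma concentration data it says: "Values that are BLQ will be set to 0 for the calculation of summary statistics". Its only rule for PK parameters concerns tlast and tmax.

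SAP 7.1.2 adds the general rule for continuous data: "Missing values will not be imputed, unless specifically stated otherwise". With fewer than 3 valid observations, only n, minimum and maximum are shown.

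**The concern.** A BLQ result at 24 hours is not an absent observation. The sample was taken and assayed, and it shows that the trough was low. Treating it as missing suits the terminal-slope regression and AUC points after tlast. Applied to Ctrough, it removes observations because they are low.

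Ctrough is the parameter that shows how much drug remains at the end of a once-daily interval. Removing low values raises the mean where BLQ results are most frequent, at the lowest dose, and so distorts the comparison across doses. The study report could also carry two different 24-hour averages from the same samples, one with zeros and one without those subjects. On Day 7 the analyst would have to choose a reading of the substitution rule, possibly after seeing the data.

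**Working it through.** **Which rule reaches a BLQ sample at tau**

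| Output | Rule | Result |
|---|---|---|
| 24 h concentration summary | SAP 7.5.2 | 0 |
| Day 1 Ctrough | SAP 7.5.1.3, then 7.1.2 | missing, not imputed |
| Day 7 Ctrough | SAP 7.5.1.3 with the optional substitution | missing; or a quantifiable predose value; or 0, if a BLQ predose sample counts as before the first measurable value |

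On Day 1, removing values only because they lie below a cut-off can only raise the expected mean. The documents give no figure to reproduce, so the size below is an illustration.

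**Inputs.** Protocol 3.5.1 predicts Cmax 35 ng/mL and AUC 303 ng/mL*h at 10 mg. Each Part B group has 6 active subjects: "In each group, 6 subjects will receive AQ280 and 2 subjects will receive placebo". Assumed: one-compartment decline, dose-proportional exposure, log-normal troughs, and the LLOQ (Protocol 7.1.2 leaves the assay details to a separate document).

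**Typical trough at 10 mg, immediate absorption**
- AUC/Cmax = 303/35 = 8.66 h; half-life = 0.693 × 8.66 = 6.0 h.
- Day 1: 35 × exp(−24/8.66) = 2.19 ng/mL.
- Steady state: 2.19/(1 − exp(−24/8.66)) = 2.33 ng/mL.

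**Effect of dropping BLQ values on Day 1.** Let s = √ln(1 + CV²) and a = ln(LLOQ/2.19)/s. Then P(BLQ) = Φ(a), and the quantifiable-only mean divided by the true mean is Φ(s − a)/(1 − Φ(a)). For a trough CV of 50% and LLOQ 1: s = 0.472, a = −1.66, P(BLQ) = 4.9%, ratio = 0.983/0.951 = 1.03.

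| LLOQ (ng/mL) | CV 50%: P(BLQ), ratio | CV 100%: P(BLQ), ratio |
|---|---|---|
| 0.1 | 0.0%, 1.00 | 0.0%, 1.00 |
| 0.5 | 0.1%, 1.00 | 3.8%, 1.03 |
| 1 | 4.9%, 1.03 | 17%, 1.16 |
| 2 | 42%, 1.30 | 46%, 1.52 |

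At 30 mg and LLOQ 2 the same formula gives 1.00 (CV 50%) and 1.07 (CV 100%), so the bias fades as dose rises. The chance that at least 1 of 6 active subjects is affected is 1 − (1 − P)⁶. At 10 mg and LLOQ 1 that is 26% (CV 50%) or 68% (CV 100%).

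**Wider variability.** A 24-hour trough lies 4 to 5 half-lives after the dose, so variation in clearance and volume is magnified. Simulations based on the same 10 mg prediction used CL/F = 10 mg/303 ng·h/mL = 33.0 L/h, half-lives of about 4.7 to 5.9 h and 20% within-subject noise. CL and V were varied separately, with CL CV 30–40%, V CV 25%, and CL–V correlation 0 or 0.8. The mean was overstated by about 0–11% at LLOQ 0.1, 1–35% at 0.5 and 9–60% at 1 ng/mL. The upper ends need uncorrelated CL and V.

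**Day 7.** At 10 mg, LLOQ 2, between-subject CV 50% and within-subject CV 20%, the mean relative to truth is:
- no substitution: 1.28
- substitution, with a BLQ predose value also missing: 1.24
- substitution, with a BLQ predose value taken as 0: 0.87

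The sign therefore depends on the reading. The effect on AUCtau is small. With C12 = 8.75 ng/mL, replacing a C24 of 0.8 by 1.2 changes the 12–24 h log-trapezoid area from 12 × 7.95/ln(8.75/0.8) = 39.9 to 12 × 7.55/ln(8.75/1.2) = 45.6. That is 5.7/303 = 1.9%.

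**The case against.** The strongest reply is that this is a small drafting gap with no demonstrated consequence.

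- **BLQ troughs may not occur.** With an LLOQ of 0.1 ng/mL or a longer terminal phase than the one-compartment value, few or none may arise. Protocol 3.5.2 places the first Part B dose in the pharmacologically active range without fixing it in mg. This stands, and makes the point conditional.
- **The larger percentages need wide trough variability.** CL/F and V/F share F, so independent draws exaggerate the spread in half-life. With a correlation of 0.8 and CL CV 40%, the overstatement at LLOQ 0.5 falls from 19–35% to 5–17%, though at LLOQ 1 it is still 18–42%. This stands as a limit on size.
- **Little depends on Ctrough.** The named Part B parameters (Protocol Table 2, SAP Table 1) are AUCtau, Cmax and, for AQ280, the accumulation ratio. SAP 7.5.3.1 does not test Ctrough. All concentrations are listed, BLQ samples stay in the concentration tables as 0, and a reduced n would be visible. This stands.
- **Zero-filling is also biased.** At LLOQ 2 and 10 mg the zero-filled mean is 0.53–0.89 of truth across the CL–V scenarios. Dropping gives 1.37–2.06 there, so zero is usually nearer, but not unbiased. This is why the median should lead.

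A reader might also infer that Part B Ctrough as a whole is computed only from quantifiable troughs and is biased upward. The documents do not support that. The Day 7 substitution can bring in a predose value or a 0, and no BLQ trough is certain to occur.

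**Conclusion.** The gap is real and minor. On Day 1 the stated rules remove a measured BLQ trough from the Ctrough summary. If any occur, the bias is upward and largest at the lowest dose. On Day 7 the direction cannot be settled from the text. The same sample is handled in one way for Ctrough and in another for the concentration table.

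The size cannot be determined without the LLOQ and the Part B doses. The illustrative ranges rest on a one-compartment model, the predicted 10 mg exposure and assumed variability. They run from nothing to about 60% for LLOQ values up to 1 ng/mL, and should not be read as an estimate for this trial. Nothing in the documents shows a named endpoint or an escalation rule that depends on the Ctrough summary.

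**What to change.** Add to SAP 7.5.1.3:

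- A BLQ result at the end of the dosing interval is an observed value. For Ctrough it is set to 0, consistent with SAP 7.5.2.
- The number of BLQ values and the median are the main Ctrough summary. No geometric mean is given for a dose and day with a BLQ value, and a note states that the zero-filled arithmetic mean is biased low when many values are BLQ.
- The Day 7 predose/tau substitution applies only when a sample was not taken or has no reportable result, not when the result is BLQ.
- BLQ results stay treated as missing for lambda-z and for AUC points after tlast.

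Ranking BLQ values lowest leaves the median exact while fewer than half are BLQ, that is, up to 2 of 6 subjects.

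The cost is a few sentences and a programming flag, settled before unblinding. No new data are needed. The one loss is the geometric mean for a dose and day with a BLQ trough.

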### **7.5.1.4. Treatment of Outliers in Pharmacokinetic Analysis**

If a value is considered to be anomalous due to being inconsistent with the expected PK profile, it may be appropriate to exclude the value from the PK analysis. However, the exclusion of any data must have strong justification and will be documented in the CSR.

Any quantifiable predose concentration value in the first treatment period will be considered anomalous and set to missing for the PK analysis. This will be set to 0 by default in Phoenix WinNonlin.

If the predose concentration is  $>5\%$  of  $C_{max}$  in the second treatment period for the food effect group (A3), all PK concentration and parameter data will be excluded from the summary statistics and statistical analysis for that period.

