The decision to proceed to the next dose group or trial part will be taken by the dose escalation committee (DEC). Dose increases between groups may be up to 5-fold for dose levels where the next dose is predicted not to surpass exposure limits of 35 ng/mL (maximum observed concentration [C_{max}]) or 303 ng/mL *h (area under the concentration-time curve [AUC]), ie, exposures corresponding to the predicted minimally pharmacologically active dose of 10 mg; but will not be more than 3-fold at any subsequent dose increment.

Part A: Single ascending dose (SAD)

Five sequential dose groups with single administration of AQ280 capsule are planned, with 1 group including a second treatment period with dose administration under fed condition to investigate food interaction. Sentinel dosing will be used in the first dose group.

The single ascending dose (SAD) portion will include:

- A screening visit from 2 days up to 5 weeks before the dose of investigational medicinal product (IMP).
- An in-clinic treatment period of 4 days which includes a 48-hour period after the dose. Eligible subjects will be randomized on Day 1 to AQ280 or placebo prior to administration.
- A safety follow-up phone call will be conducted 1 week (± 2 days) after dose administration.

Dose administration will occur on Day 1.

Safety assessments will include adverse event (AE) reporting, vital signs, electrocardiograms (ECGs), clinical laboratory tests, and physical examination.

Blood samples to determine the PK of AQ280 and its main metabolite, AQ282, will be collected from predose up to 48 hours postdose.

Part B: Multiple ascending dose

Three sequential dose groups are planned, with subjects dosed once daily (QD).

The multiple ascending dose (MAD) portion will include:

- A screening visit from 2 days up to 5 weeks before the first dose of IMP.
- An in-clinic treatment period of 9 days which includes a 48-hour period after the last dose. Eligible subjects will be randomized on Day 1 to AQ280 or placebo prior to administration.
- A safety follow-up visit will be conducted 1 week (± 3 days) after the final dose.

For all subjects, dosing is planned to be QD on Days 1 to 7, inclusive, at approximately the same time each morning. The total daily dose administered will not exceed an exposure shown to be safe and well tolerated in Part A.

Safety assessments will include AE reporting, vital signs, ECGs, clinical laboratory tests, and physical examination.

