Appendix 3: Total Blood Volume

The following blood volumes will be withdrawn for each subject in Part A (single ascending dose).

	Volume per blood sample (mL)	Maximum number of blood samples	Total amount of blood (mL)
Full clinical laboratory evaluations	9.3	4	37.2
Serology	3.5	1	3.5
Quantiferon™ TB Gold test	4	1	4
AQ280/AQ282 PK ^a	4	17	68
CCI [REDACTED]	2	8	16
CCI [REDACTED] PD ^{a,b}	2.5	8	20
Total:			148.7

Abbreviations: PD = pharmacodynamics; PK = pharmacokinetics; TB = tuberculosis.

^a Includes 3 potential additional samples.

^b Additional assessments performed outside of full clinical laboratory evaluations.

The following blood volumes will be withdrawn for each subject in Part A (single ascending dose) for the food effect evaluation.

	Volume per blood sample (mL)	Maximum number of blood samples	Total amount of blood (mL)
Full clinical laboratory evaluations	9.3	7	65.1
Serology	3.5	1	3.5
Quantiferon™ TB Gold test	4	1	4
AQ280/AQ282 PK ^a	4	34	136
CCI [REDACTED]	2	8	16
CCI [REDACTED] PD ^{a,b}	2.5	8	20
Total:			244.6

Abbreviations: PD = pharmacodynamics; PK = pharmacokinetics; TB = tuberculosis.

^a Includes 3 potential additional samples per treatment period.

^b Additional assessments performed outside of full clinical laboratory evaluations.

If extra blood samples are required, the maximum blood volume to be withdrawn per subject will not exceed 550 mL.

The following blood volumes will be withdrawn for each subject in Part B (multiple ascending dose).

	Volume per blood sample (mL)	Maximum number of blood samples	Total amount of blood (mL)
Full clinical laboratory evaluations	9.3	7	65.1
Serology	3.5	1	3.5
Quantiferon™ TB Gold test	4	1	4
AQ280/AQ282 PK ^a	4	32	128
CCI [REDACTED] [REDACTED] [REDACTED] PD ^{a,b}	2	5	10
CCI [REDACTED] [REDACTED] PD ^{a,b}	2.5	5	12.5
CCI [REDACTED] PD ^{a,b}	4	5	20
Total:			243.1

Abbreviations: CCI

PD = pharmacodynamics; PK = pharmacokinetics;

TB = tuberculosis.

^a Includes 3 potential additional samples.

^b Additional assessments performed outside of full clinical laboratory evaluations.

If extra blood samples are required, the maximum blood volume to be withdrawn per subject will not exceed 550 mL.

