Weight	X	X										X	X	X	
Safety ECG	X	X	X*		X*		X*		X*	X*	X*	X	X	Day 1: Predose (triplicate), t_{max}^a . Days 3 and 5: Predose. Day 7: Predose, t_{max}^a . Day 8: 24 hours post Day 7 dose. Day 9: 48 hours post Day 7 dose.	

Visit Name	Screening	Check- in	Treatment period									Follow-up	Early Termination (if applicable)	Comment (*)
Visit No.	1		2									3		
Day No. Visit window (calendar days)	-35 to -2	-1	1	2	3	4	5	6	7	8	9	14 ±3 days		
All hematology, coagulation, and clinical chemistry	X	X		X*		X*			X*		X*	X	X	Day 2: 24 hours postdose (collected prior to dose on Day 2). Days 4 and 7: Predose. Day 9: 48 hours post Day 7 dose.
Urinalysis	X		X*		X*			X*		X*	X*	X	X	Days 1, 4, and 7: Predose. Day 9: 48 hours post Day 7 dose.
Urine pregnancy test*		X										X	X	Only female subjects.
Adverse events	X		X									X	X	
PK/PD assessments														
PK blood sample*			X*	X*	X*	X*	X*	X*	X*	X*	X*	X		See footnote b. Day 1: Predose, 0.25, 0.5, 1, 1.5, 2, 3, 4, 6, 8, and 12 hours postdose. Day 2: 24 hours postdose. Days 3 through 6: Predose. Day 7: Predose, 0.25, 0.5, 1, 1.5, 2, 3, 4, 6, 8, and 12 hours postdose. Day 8: 24 hours post Day 7 dose. Day 9: 48 hours post Day 7 dose.
CCI [REDACTED]			X*						X*	X*	X*			See footnote c. Day 1: Predose (spot collection), 0-8, 8-16, and 16-24 hours postdose. Day 7: 0-8, 8-16, and 16-24 hours postdose. Day 8: 24-36 hours post Day 7 dose. Day 9: 36-48 hours post Day 7 dose.

Visit Name	Screening	Check- in	Treatment period									Follow-up	Early Termination (if applicable)	Comment (*)
Visit No.	1		2									3		
Day No. Visit window (calendar days)	-35 to -2	-1	1	2	3	4	5	6	7	8	9	14 ±3 days		
CCI [REDACTED]				X*		X*			X*	X*	X*			Day 1: Predose. Day 4: Predose (analyzed as part of scheduled hematology and clinical chemistry evaluations). Day 7: Predose (analyzed as part of scheduled hematology and clinical chemistry evaluations). Day 8: 24 hours post Day 7 dose. Day 9: 48 hours post Day 7 dose (analyzed as part of scheduled hematology and clinical chemistry evaluations).
CCI [REDACTED]			X*		X*			X*	X*	X*				Days 1, 4, and 7: Predose. Day 8: 24 hours post Day 7 dose. Day 9: 48 hours post Day 7 dose.

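### SAP 7.5.1.4 does not limit its removal of quantifiable predose values to the sample before the first dose, so as written it also covers the Part B Day 3 to Day 7 predose samples

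*SAP*

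**What the plan says.** SAP 7.5.1.4 opens with a discretionary provision for outliers, conditioned as follows: "If a value is considered to be anomalous due to being inconsistent with the expected PK profile". A mandatory rule comes next: "Any quantifiable predose concentration value in the first treatment period will be considered anomalous and set to missing for the PK analysis". The consequence in the software is then given: "This will be set to 0 by default in Phoenix WinNonlin". The section closes with a carryover rule that is expressly confined to the second period of the food effect group, A3.

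Other text that bears on the rule:

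- **Protocol Synopsis, Part B:** "An in-clinic treatment period of 9 days which includes a 48-hour period after the last dose". Part B therefore has one treatment period.
- **Protocol Appendix 6, Part B PK blood samples:** "Days 3 through 6: Predose. Day 7: Predose". On Days 3 to 6 no other PK sample is scheduled.
- **SAP 7.5.1.3:** the zero default for an absent predose value carries a limit, worded thus: "following a single dose (Part A) or Day 1 dose (Part B) it will be set to 0 by default within Phoenix WinNonlin". The same section allows the Day 7 predose value and the end-of-interval value to stand in for each other when one is missing.
- **SAP 7.5.2:** concentrations deemed anomalous are flagged in the listings and left out of the summary statistics, while values below the limit of quantification (BLQ) enter as 0.
- **SAP 7.1.2:** with fewer than 3 valid observations, "summary statistics will not be calculated, with the exception of" n, minimum and maximum.

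**The concern.** A quantifiable value before the first dose is implausible, and removing it is sensible. A quantifiable predose value on Days 3 to 7 of daily dosing is what the design expects. Protocol 3.4 says that Part B is meant to reach steady state and hold it for several days, and these samples are the scheduled evidence for Days 3 to 6. The rule as written does not separate the two situations.

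It also cannot be followed together with 7.5.1.3. That section confines the zero default to Part A and Part B Day 1, and it lets a missing Day 7 predose value be replaced by the end-of-interval concentration; 7.5.1.4 would set it to 0. In the other direction, 7.5.1.3 lets the Day 7 predose value replace a missing end-of-interval value, which presupposes that it is valid data.

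At stake are the Part B predose summaries and the mean figure across all days. No data would be lost, because all concentrations are listed.

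**Working it through.** The plan gives no figure on this point to reproduce. The check counts the samples that the wording reaches, applies the SAP rules to one summary cell, and bounds the effect on Day 7 AUC.

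**1. Samples reached (Protocol Appendix 6)**

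- Scheduled Part B PK timepoints: Day 1 = 11 (predose plus 10), Day 2 = 1, Days 3 to 6 = 4, Day 7 = 11, Day 8 = 1, Day 9 = 1. Total = 29.
- Cross-check with Protocol Appendix 3: the maximum is 32 samples, with the footnote "Includes 3 potential additional samples"; 32 − 3 = 29.
- Predose samples after the first dose: Days 3, 4, 5, 6 and 7 = 5. The Day 2 sample is labelled 24 hours postdose and is not counted. 5/29 = 17.2%.
- Summary cells per analyte: 5 days × 3 groups = 15. Values per analyte: 15 × 6 active subjects = 90, a ceiling reached only if every value is quantifiable.

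**2. One cell of 6 active subjects**

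With k quantifiable values, the literal rule keeps n = 6 − k values. All of them are BLQ and entered as 0, and a mean is given only if n ≥ 3. The last column shows the mean if the values are kept, for illustration with every quantifiable trough set to 1 unit: k/6.

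| Quantifiable (k) | n summarised | Shown under the literal rule | Mean if kept |
|---|---|---|---|
| 0 | 6 | mean 0 | 0 |
| 1 | 5 | mean 0 | 0.17 |
| 2 | 4 | mean 0 | 0.33 |
| 3 | 3 | mean 0 | 0.50 |
| 4 | 2 | no mean; minimum and maximum 0 | 0.67 |
| 5 | 1 | no mean; minimum and maximum 0 | 0.83 |
| 6 | 0 | n = 0 | 1.00 |

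No pattern gives a non-zero mean under the literal rule.

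**3. Gap in the mean figure across all days**

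The last unaffected point before the gap is 24 h after the first dose. The Day 7 dose falls at 6 × 24 = 144 h, so the next unaffected point is 144.25 h. Gap = 144.25 − 24 = 120.25 h. The profile ends at 144 + 48 = 192 h. 120.25/192 = 62.6%.

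**4. Day 7 AUC over the dosing interval**

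- *Bound.* If the predose value Cpre is read as 0 and concentrations rise to the first sample at 0.25 h, the linear rule loses 0.5 × 0.25 h × Cpre = 0.125 h × Cpre. With Cpre no larger than the interval average Cavg, and AUC = 24 h × Cavg, the loss is at most 0.125/24 = 0.52%.
- *Model.* One-compartment oral model, 7 doses at 24 h intervals, scheduled sampling times, linear-up/log-down. The half-life is redacted, so values of 4, 8, 12, 24 and 48 h and absorption rates of 0.5, 1, 2 and 4 per hour were assumed. Setting predose to 0 changes AUC by −0.036% (4 h, 4 per hour) to −0.432% (48 h, 0.5 per hour). Replacing it with the end-of-interval value changes AUC by at most 0.018%.

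**The case against.** The strongest reply is that the narrow reading is the natural one. In the legible SAP text, treatment period is used for Part A, and Part B is described by days; the term reaches Part B only through the protocol. The sentence stands directly before the A3 second-period rule, which suggests a contrast between no prior drug in Period 1 and possible carryover in Period 2. The section ties anomalous to departure from the expected profile and asks for strong justification for any exclusion. On that reading, 7.5.1.3 and 7.5.1.4 agree.

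The effect on summaries is also inferred. The rule speaks of the PK analysis, whereas the A3 rule expressly names summary statistics. The link runs through the word anomalous in 7.5.2, which could be read as covering only case-by-case judgements. The TFL shells, which hold the display details, are not among the documents.

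Much of this stands. The first-dose intent is likely, and the percentages describe a literal application, not an expected loss. What it does not supply is the limit itself. The protocol does call the Part B stay a treatment period, the rule is mandatory where the outlier provision before it is discretionary, and no other text carries the Day 1 restriction into 7.5.1.4. SAP Section 1 wants the plan final before programming begins, so the written rule should match the intent.

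**Conclusion.** The concern holds as a minor error of wording: the rule lacks its first-dose limit and conflicts with 7.5.1.3 as written. It is not a finding that the team would discard trough values.

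The effect on summaries rests on two readings: that the Part B stay counts as a first treatment period, and that values declared anomalous in 7.5.1.4 fall under the exclusion in 7.5.2. Without the second, the Day 3 to 6 values stay in the summaries, and what remains is the Day 7 parameter calculation, with a change of at most 0.52% in AUC. That bound assumes a predose value no higher than the interval average and concentrations rising to 0.25 h.

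On either reading, the legible Part B PK endpoints (accumulation ratio, AUC over the dosing interval, Cmax), the Day 7 end-of-interval concentration, the individual figures and the listings are essentially unaffected.

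**What to change.** In SAP 7.5.1.4, limit the sentence to the predose sample taken before the first dose, naming Part A Period 1 Day 1 and Part B Day 1. Add that quantifiable Part B predose values after Day 1 are retained in the PK analysis and in the concentration summaries and figures.

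The cost is one phrase and one short statement in the SAP. The protocol, sampling schedule and data collection do not change, and the safeguard against implausible values before the first dose stays in place. The section then agrees with 7.5.1.3.
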